5.1.3 Administration of Imatinib mesylate

Imatinib will be supplied by Novartis. Imatinib is available in 100 mg and 400 mg scored capsule. Preferentially and unless otherwise clinically indicated, 400mg capsule will be used. The investigator should instruct the patient to take the study drug exactly as prescribed (promote compliance) and to notify the Investigator of any deviations. Patients will be instructed to record their daily study drug administration in the patient diary provided to them. Imatinib will be dosed at 400 mg once a day by mouth. Because of the potential for intestinal irritation, the capsule should be taken during a meal and with a large glass of water (8 oz) to minimize the chance of irritating the esophageal and/or gastric mucosa. Patients should keep normal eating habits; however, low-fat (i.e. continental) breakfast is recommended avoiding xanthine (e.g. caffeine) or grapefruit containing food or beverages. Minimum of 1h should be allowed between last drug intake and going to bed. If vomiting occurs, no additional trial medication should be taken that day in an effort to replace the material that has been vomited. If a dose of imatinib is missed, the subject should take the dose as soon as possible, but only if there are 12 or more hours remaining before the next dose is due. If the next dose is due in less than 12 hours, the subject should skip the missed dose and take the next dose as scheduled. A study medication diary will be completed by the patients for each dose of Imatinib.

Instructions for dose modifications can be found in Section 9.

5.2 BGJ398

5.2.1 Mechanism of Action:

BGJ398 is an orally bioavailable, potent and selective inhibitor of the fibroblast growth factor receptors (FGFRs). The FGFR family of receptor tyrosine kinases (RTKs) consists of four members (FGF-R1, FGF-R2, FGF-R3, FGF-R4), which serve as the high affinity receptors for 22 FGF ligands. These are pleiotropic growth factors that control cell proliferation, migration, angiogenesis, apoptosis and differentiation and are involved in both developmental and adult tissue homeostasis. More recently, cancer epidemiological and molecular studies have reported various genetic alterations including gene amplifications, mutations and chromosomal translocations, as well as aberrant protein expression for this family of RTKs and ligands. Further, their link to cancer dependence has been established preclinically by means of loss of function approaches. Preclinical research studies have shown that BGJ398 selectively suppresses FGFR signaling and proliferation in cancer cells with FGFR dependency and respectively, the tumor growth of mouse and rat xenograft models associated with aberrant FGFRs expression/activation. In addition to a direct effect on the tumor cells, BGJ398 has an effect on endothelial cells by blocking bFGF-induced angiogenesis, thus providing an alternative mechanism to inhibit tumor growth. On this basis, targeted inhibition of FGFRs can be exploited for therapeutic gain.

5.2.2 Formulation, Storage and Packaging

BGJ398 will be provided by Novartis as film-coated capsule for oral use of dosage strength of 25mg and 100mg. Study drug must be received by a designated person at the study site, handled and stored safely and properly, and kept in a secured location to which only the investigator and designated assistants have access. Upon receipt, BGJ398 should be stored according to the instructions specified on the drug labels. Study medication will be dispensed by an authorized person at the investigator's site.

MEMORIAL SLOAN-KETTERING CANCER CENTER
IRB PROTOCOL

IRB#: 14-140 A (7)

5.2.3 Administration of BGJ398

BGJ398 will be taken orally, using treatment schedule A (once a day for 21 days on, 7 days off) or treatment schedule B (once daily for 7 days on, 21 days off) repeating in 28 day cycles. Patients should be instructed to take the daily dose of BGJ398 in the morning, at approximately the same time each day (24 ± 2 hour interval). Patients should consume a light breakfast each day (e.g., non-grapefruit-based juice, toast and jam). This should be followed by a 2 hour fast, after which the doses of study drug should be taken. Patients should continue to fast for 1 hour after the administration of study drug.

BGJ398 should be taken with a large glass of water (~250 mL) and consumed over as short a time as possible. Patients should be instructed to swallow the capsules whole and not chew them. If for any reason a breakfast was not consumed prior to taking the dose the patient should take the dose with a full glass of water, and continue to fast for an hour after taking the dose. If the patient forgets to take the scheduled dose in the morning, he/she should not take the dose more than 2 hours after the usual time and should continue treatment the next day. Any doses that are missed should be skipped altogether and should not be replaced or made up at the next scheduled dosing.

If vomiting occurs following the dosing of study drug, re-dosing is not permitted that same day. Dosing should resume the next day. BGJ398 is characterized by pH-dependent solubility, and therefore, medicinal products that alter the pH of the upper gastro-intestinal tract may alter the solubility of both compounds, and limit bioavailability. These agents include, but are not limited to, proton-pump inhibitors (e.g., omeprazole), H₂-antagonists (e.g., ranitidine) and antacids. Therefore, BGJ398 should be dosed at least 2 hours before or 10 hours after dosing with a gastric protection agent. Patients must avoid consuming Seville oranges or juice, grapefruit, grapefruit juice, grapefruit hybrids, or pummelos from 7 days prior to the first dose of study medication through the end of study participation. This is due to a potential CYP3A4 interaction with study medication. Normal oranges and orange juice are allowed.

The investigator or responsible site personnel should instruct the patient to take the study drug exactly as prescribed to promote compliance. All dosages prescribed and dispensed to the patient and all dose changes or missed doses during the study must be recorded. A study medication diary will be completed by the patients for each dose of BGJ398. Patients will be instructed to return unused study drug to the site at the end of each cycle.

6.0 CRITERIA FOR SUBJECT ELIGIBILITY

6.1 Subject Inclusion Criteria

Patients eligible for inclusion in this study have to meet **all** of the following criteria:

Inclusion criteria:

- Patients must have pathologically confirmed GIST.
- In the Phase Ib portion, must have locally advanced or metastatic GIST and have progressed on imatinib.
- In the Phase II portion, patients must be newly diagnosed or imatinib treatment naïve in the advanced/metastatic setting. Prior adjuvant imatinib therapy is allowed as long as disease

MEMORIAL SLOAN-KETTERING CANCER CENTER IRB PROTOCOL

IRB#: 14-140 A (7)

recurrence was documented ≥ 90 days after last dose of imatinib and imatinib has not yet been restarted.

- Patients must be at least 18 years of age.
- Disease must be measurable by RECIST 1.1.
- ECOG Performance Status 0 or 1.
- Adequate renal, hepatic, and hematologic function as the following: Serum Creatinine ≤ 1.5 mg/dL, Total Serum Bilirubin ≤ 1.5 x upper limit of normal (ULN) unless due to Gilbert's Disease, Serum AST (SGOT) and/or ALT (SGPT) ≤ 2.5 x ULN (or ≤ 5.0 x ULN if considered due to tumor), ANC $\geq 1500/\text{mm}^3$, Platelets $\geq 100,000/\text{mm}^3$, and hemoglobin $\geq 10\text{g/dL}$.
- Patients of childbearing potential must have a negative blood pregnancy test within 14 days of treatment. Patients must agree to use a reliable barrier method of birth control during and for 3 months following the last dose of study drug.
- Patient must have adequate cardiac function (left ventricular ejection fraction (LVEF) $\geq 50\%$ as determined by a multigated acquisition (MUGA) scan or echocardiogram; and QTc interval ≤ 480 ms by Fridericia's formula (QTcF).
- Patient must be able to take oral medications.
- Patients must sign an informed consent document.

6.2 Subject Exclusion Criteria

Patients meeting any of the following criteria are excluded from the study:

Exclusion criteria:

- For phase I, prior intolerance to imatinib at a dose of 400 mg daily.
- For phase II, any receipt of cytotoxic, biologic, or immune therapy aimed to treat GIST except for adjuvant imatinib systemic therapy that concluded at least 90 days prior to registration. For Phase I, patients are eligible regardless of prior therapy.
- Chronic liver disease (e.g., cirrhosis)
- Known positive serology for HIV, active Hepatitis B, and/or active Hepatitis C infection.
- Patients have a history or current evidence of Central Serous Retinopathy (CSR) or retinal vein occlusion (RVO) or major predisposing factors to CSR or RVO (e.g. uncontrolled glaucoma or ocular hypertension) in the opinion of the study ophthalmologist.
- History of retinal degenerative disease
- Active corneal disorder or keratopathy (e.g. corneal abrasion, bullous keratopathy)
- Severe and/or uncontrolled medical disease, including:
 - Uncontrolled diabetes mellitus (A1c > 8)
 - Chronic Kidney Disease Stage III or higher (Creatinine Clearance $< 60\text{mL}/\text{min}/\text{m}^2$ by Modified Diet in Renal Disease (MDRD) calculation)
 - Active, uncontrolled infection
- Known active brain metastasis unless they have been treated and shown documented radiographic stability for 28 days.
- Known other active malignancy (other than malignancies which the investigator determines are unlikely to interfere with treatment and safety analysis).
- Patients have clinically significant cardiovascular disease, including any of the following

MEMORIAL SLOAN-KETTERING CANCER CENTER IRB PROTOCOL

IRB#: 14-140 A (7)

- Any history of acute coronary syndrome including myocardial infarction, stable or unstable angina, CABG, coronary angioplasty or stenting, or known obstructive coronary artery disease
- Symptomatic chronic heart failure (New York Heart Association Criteria, Class II-IV)
- Evidence of clinically significant cardiac arrhythmias and/or conduction abnormalities < 6 months prior to screening except atrial fibrillation (AF) and paroxysmal supraventricular tachycardia (PSVT)
- Any history of thrombotic cerebrovascular accident or other arterial thrombosis
- Uncontrolled arterial hypertension (systolic blood pressure >155 mmHg or diastolic >95 mmHg) despite appropriate medical therapy.
- History and/or current evidence of uncontrolled endocrine alterations of calcium/phosphate homeostasis, e.g., parathyroid disorders, history of parathyroidectomy, tumor lysis, tumoral calcinosis, etc.
- Impairment of gastrointestinal function or gastrointestinal disease (e.g., uncontrolled ulcerative disease; uncontrolled nausea, vomiting, diarrhea; chronic malabsorption syndrome).
- Patients with major surgery within 3 weeks prior to study entry or who have not recovered from side effects of such procedure.
- Women who are pregnant or lactating.
- Sexually active males, unless they use a condom during intercourse while taking the drug and for 15 days after stopping treatment. They should not father a child in this period. A condom is required to be used also by vasectomized men in order to prevent delivery of the drug via seminal fluid.
- Patients with any significant history of non-adherence to medical regimens or with inability to grant reliable informed consent.

7.0 RECRUITMENT PLAN

Both men and women and members of all races and ethnic groups are eligible for this trial. The clinical trial will be listed on the clinicaltrials.gov website and on the websites of participating institutions. Patients will be identified through internal referrals and external referrals by Medical and Surgical Oncologists nationally and internationally. Patients will be recruited through the Sarcoma Disease Management Team of the Memorial Sloan-Kettering Cancer Center, Dana Farber Cancer Institute and MD Anderson Cancer Center. The Sarcoma service and the Sarcoma Disease Management Team each hold weekly interdepartmental meetings to identify study participants for open clinical trials. We will also discuss the trial and patient recruitment with several GIST patient support groups.

Patients will be recruited through the Sarcoma Disease Management Team of the participating institutions.

8.0 PRETREATMENT EVALUATION

Patients will need to have the following tests and procedures prior to entering the study:

Within 4 weeks of study start:

MEMORIAL SLOAN-KETTERING CANCER CENTER IRB PROTOCOL

IRB#: 14-140 A (7)

- Informed Consent
- Tumor imaging - CT Chest/Abdomen/Pelvis preferable
- Confirmation of disease (A biopsy will be required if patients do not have enough archived tissue to make treatment decisions). A portion of this biopsy will be collected for research purposes only after a pathological diagnosis has been made and informed consent has been obtained.
- Ophthalmology examination
- Tumor biopsy: After consent, and prior to treatment, 20 patients enrolled on the Phase II portion of the study across all sites will have a dedicated open incisional or core biopsy of their disease (see section 9.1 for detailed description of biopsy selection process). After biopsies on 20 patients are obtained, consent to a biopsy will not be mandated for enrollment. However, consent to research biopsies in subsequent patients will be encouraged if funding exists.

Within 2 weeks of study start:

- Demographics
- B-HCG (if applicable)
- Medical History
- Concurrent Medication
- Physical Exam
- Vital Signs
- Height
- Weight
- Performance Status (ECOG)
- CBC with differential, platelets
- Blood Chemistry--Comprehensive panel- (Albumin, total bilirubin, bicarbonate, BUN, calcium, chloride, creatinine, sodium, glucose, potassium, total protein, sodium, alkaline phosphatase, SGOT [AST], SGPT [ALT]) plus LDH, creatinine phosphokinase (CK), magnesium, phosphorus, amylase, and lipase.
- TSH
- Hepatitis B serology—(Hep B surface antigen, Hep B surface antibody and Hep B core Antibody)
- EKG
- Urinalysis
- Baseline FDG PET scan (Phase II study only)
- Echocardiogram or MUGA

Please see Study Calendar in Section 10.0 for more information.

9.0 TREATMENT/INTERVENTION PLAN

Treatment will be administered on an outpatient basis. Reported adverse events and potential risks are described in Section 11. Appropriate dose modifications of imatinib and BGJ398 are described in section 9.2. No investigational or commercial agents or therapies other than those described below may be administered with the intent to treat the patient's malignancy.

MEMORIAL SLOAN-KETTERING CANCER CENTER IRB PROTOCOL

IRB#: 14-140 A (7)

Imatinib will be self administered orally by the patient on a daily basis throughout the treatment cycle. The standard treatment dose is 400 mg PO QD. 400 mg capsule will be used unless otherwise specified by the treating physician. BGJ398 will be taken at the RP2D and treatment schedule chosen from the Phase Ib portion of the trial. The RP2D selected may be lower than the MTD based on PK data and clinical tolerance beyond Cycle 1. BGJ398 is taken daily for a duration determined by the treatment schedule appropriate for the given dose level. In the event of dose delays of BGJ398, Day 1 of the following cycle will be defined as the day that BGJ398 is restarted. A pill diary for both medications will be provided and recorded (Appendix B). This will be used to assure compliance with the regimen.

On the Phase Ib portion, the timing of pharmacokinetic sample collections will be dependent on the treatment schedule onto which that patient is enrolled. For treatment schedule A pharmacokinetic samples will be drawn on Cycle 1, Day 1 at the following timepoints: 0, 1, 2, 4, 6, 8, and 24 hrs; and Cycle 1, Day 21 at the following timepoints: 0, 1, 2, 4, 6, and 8 hours. For treatment schedule B pharmacokinetic samples will be drawn on Cycle 1, Day 1 at the following timepoints: 0, 1, 2, 4, 6, 8, and 24 hrs; Cycle 1, Day 7 at the following timepoints: : 0, 1, 2, 4, 6, and 8 hours, Cycle 1, Day 15 at timepoint 0hr and Cycle 1, Day 21 at timepoint 0hr.

After consent, and prior to treatment, the first 20 patients enrolled on the Phase II portion of the study across all sites will have a dedicated open incisional or core biopsy of their disease. All biopsies will be performed at MSKCC or other participating institutions. Biopsies on subsequent patients will not be mandated, but encouraged if additional funding is identified. A patient may be excused from this biopsy requirement if tissue is not accessible or if investigator determines that the patient should not undergo this biopsy. If this occurs, a biopsy will be mandated in additional patients to ensure that at least 20 participants undergo a biopsy. Upon initiation of treatment, patients who underwent a pre-treatment biopsy will undergo a second biopsy after one week (C1D8) of combination of BGJ398 and imatinib treatment and at time of disease progression. All patients will undergo baseline staging FDG PET and body imaging and repeat FDG PET scans during week three of the combination therapy of treatment (C1D21) as part of standard of care. Four weeks of treatment (28 days) will be considered one cycle. Imaging with standard CT scans and response evaluations will occur every 8 weeks for the first 32 weeks regardless of treatment interruption and then on Day 1 of every 3rd cycle thereafter.

All participants on the Phase II portion will have a 2-week lead in of imatinib. Blood will be drawn at the end of this period to establish steady-state imatinib serum trough levels. After blood for imatinib levels are obtained, BGJ398 at the established Phase II dose and treatment schedule will be added to the regimen. The start of the combination therapy will mark the beginning of cycle 1 (Day 1 cycle 1). The initiation of BGJ398 will not be contingent on the imatinib level; rather, BGJ398 can be started after the blood draw from imatinib levels is performed. Blood will be drawn again approximately 3-5-weeks after the initiation of the combination therapy to establish the steady-state imatinib serum trough levels in the presence of BGJ398.

9.1 Dose Rationale:

Phase Ib: The primary endpoint of the phase 1b portion of this study is to determine the maximum tolerated dose (MTD) and the Recommended Phase 2 Dose (RP2D) and treatment schedule of BGJ398 administered in combination with imatinib in patients with GIST. The phase Ib will be pursued in standard 3+3 format, based on toxicities encountered during the first cycle of therapy.

**MEMORIAL SLOAN-KETTERING CANCER CENTER
IRB PROTOCOL**

IRB#: 14-140 A (7)

The first three patients will be enrolled at Dose level 1 (Table 1, see section 1) using treatment schedule A. Dose level 1 is chosen based on the standard of care imatinib dose of 400 mg daily in the advanced GIST patient population, and an intermediate dose level of BGJ398 (75 mg daily). This dose is below the BGJ398 MTD of 125 mg daily identified in phase I trials as monotherapy. BGJ398 dose level 1 to -2 will be administered using a schedule of BGJ398 taken daily for 3 weeks followed by one week off and imatinib taken daily throughout the 4 week cycle period (treatment schedule A).

The maximum pace of dose escalation within each cohort is outlined in Table 2. Expansions of lower dose levels may be made based on safety and tolerance considerations at the MSKCC Principal Investigator's discretion, and the selected RP2D may be lower than the MTD defined below. If dose level 1 is not found to be tolerable, then the next cohort will be enrolled at dose level -1. If dose level -1 is not found to be tolerable, then the next cohort will be enrolled at dose level -2. If dose level -2 is not found to be tolerable, then the study may be terminated based on discussions with the MSKCC Principal Investigator. If 0-1 of 6 patients experience a DLT on dose level 3, this will be the RP2D.

Table 2:

Number of Patients with DLT at a Given Dose Level	Escalation Decision Rule
0 out of 3	Enter 3 patients at the next dose level.
1 out of 3	Enter at least 3 more patients at this dose level. 
 • If 0 of these additional 3 patients experience DLT (1/6 total), proceed to the next dose level. • If 1 or more of this group suffer DLT ($\geq 2/6$ total), then dose escalation is stopped, and this dose is declared the MTD. Three (3) additional patients will be entered at the next lowest dose level if only 3 patients were treated previously at that dose.
≥ 2	Dose escalation will be stopped. This dose level will be declared the MTD. Three (3) additional patients will be entered at the next lowest dose level if only 3 patients were treated previously at that dose.
≤ 1 out of 6 at highest dose level below the MTD	This is generally the recommended phase 2 dose. At least 6 patients must be entered at the recommended phase 2 dose (RP2D).

Using treatment schedule A, if dose level 1 to -2 is identified as the MTD and concern exists regarding therapeutic activity of BGJ398 at this dose level, expansions with higher dose levels (1 to 3) may be considered at the MSKCC PI's discretion, with modification of the treatment schedule. In this setting BGJ398 will be administered daily for one week followed by 3 weeks off and imatinib will be taken

**MEMORIAL SLOAN-KETTERING CANCER CENTER
IRB PROTOCOL**

IRB#: 14-140 A (7)

daily throughout the 4 week cycle period (treatment schedule B). The higher dose level expansion will start by enrolling 3 patients into a cohort, at dose level 1, using treatment schedule B.

When using treatment schedule B the maximum pace of dose escalation within each cohort is outlined in Table2.

Upon documentation of the RP2D dose and treatment schedule of the combination, the phase II trial will open and all subsequent patients enrolled will initiate treatment at that dose and treatment schedule with any subsequent dose modifications as outlined below.

Toxicity will be assessed using the NCI CTCAE (version 4.03) unless otherwise specified. Dose Limiting Toxicity (DLT) is defined as an unexpected adverse event (AE) or abnormal laboratory value assessed as at least possibly related to the study medication, which occurs ≤ 28 days (1 cycle) following the first dose of BGJ398 (cycle 1), and meets any of the criteria listed in Table 3. Please note plasma assessments may substitute for serum assessments per local laboratory standards.

Table 3: Criteria for defining dose-limiting toxicities

TOXICITY	DLT CRITERIA
Hematology	CTCAE grade 4 neutropenia lasting more than 7 consecutive days
	CTCAE grade 4 thrombocytopenia
	CTCAE Grade 3 or 4 neutropenia with fever (temperature $\geq 38.5^{\circ}\text{C}$)
Skin and subcutaneous tissue disorders	Rash, HFSR (Hand Foot Skin Reaction) or photosensitivity CTCAE Grade 3 > 7 consecutive days despite skin toxicity treatment (as per local practice)
	Rash, HFSR or photosensitivity CTCAE Grade 4
Eye disorders	CSR (Central Serous Retinopathy) CTCAE Grade 2 for > 14 consecutive days confirmed by ophthalmologic examination
	CSR (Central Serous Retinopathy) CTCAE Grade ≥ 3 , confirmed by ophthalmologic examination
	Retinal disorder other than CSR (retinal detachment/tear, retinal vascular disorder, retinopathy other) CTCAE Grade ≥ 2 confirmed by ophthalmologic examination
	Visual disturbances without ocular (retinal) changes: Blurred vision, Flashing lights, Floaters, Corneal abnormalities CTCAE Grade ≥ 3
Gastro-intestinal	\geq CTCAE grade 3 nausea or vomiting ≥ 48 hrs despite optimal anti-emetic therapy
	\geq CTCAE grade 3 diarrhea ≥ 48 hrs despite optimal anti-diarrhea treatment
	Pancreatitis \geq CTCAE grade 3
Hepato-biliary	\geq CTCAE grade 3 total bilirubin
	\geq CTCAE grade 3 ALT (isolated increases in AST without concomitant increases

**MEMORIAL SLOAN-KETTERING CANCER CENTER
IRB PROTOCOL**

IRB#: 14-140 A (7)

	in ALT will not be considered dose-limiting, because of the non-specific nature of AST)
	Serum alkaline phosphatase CTCAE Grade 4 > 7 consecutive days
Investigations (Metabolic)	Serum Lipase and/or serum amylase (asymptomatic) CTCAE grade 3 for > 7 consecutive days Serum Lipase and/or serum amylase (asymptomatic) CTCAE grade 4 Symptomatic serum lipase and/or serum amylase ≥ CTCAE grade 3
ECG QT Interval	QTcF interval ≥ 501 ms on at least two separate ECGs
Renal	Serum creatinine > 2x ULN Serum Phosphorous that requires dose interruption of BGJ398 for >14 days of first 21 days of Cycle 1
Non-hematologic events	≥ CTCAE grade 3, except for the exclusions noted below
Exceptions to DLT criteria	Grade 3 alopecia
	< 5 days of CTCAE grade 3 fatigue
	< 5 days of CTCAE grade 3 edema
	Grade 3 laboratory abnormalities that are responsive to oral supplementation or deemed by the investigator to be clinically insignificant
CTCAE version 4.03 will be used for all grading. Optimal therapy for vomiting or diarrhea will be based in institutional guidelines, with consideration of the prohibited medications listed in this protocol.	

Phase II: The RP2D doses and treatment schedule defined in the phase Ib clinical trial will be used to conduct the phase II portion of the study.

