The primary goal of the phase Ib study is to assess the tolerability and safety of the combination therapy. Once the highest tolerable dose is identified or the clinical doses of imatinib (400 mg daily) and BGJ398 (125 mg qd – three weeks on and one off) are reached, the phase II portion of the study will be initiated. The primary endpoint of the phase II portion is to assess Response Rate (RR) (complete response (CR) + partial response (PR)) by RECIST 1.1.

The phase Ib portion of the study will be performed in standard 3+3 fashion. The phase Ib portion of the study will be open to all patients with locally advanced or metastatic GIST who have progressed on imatinib. An initial cohort of three eligible patients with locally advanced or metastatic GIST will initiate treatment with BGJ398 at 75 mg daily (three weeks on and one off) and imatinib at 400 mg daily for 4 weeks (1 cycle). Depending on the toxicity, dose levels of imatinib (400 mg daily) + BGJ398 will be investigated as outlined below (Table 1). As imatinib 400 mg PO QD is standard of care for metastatic GIST, this dose will remain constant (barring individual dose modifications outlined in section 9.2a).

Table 1: The dose escalation schema:

Dose Level	Imatinib	BGJ395
-2	400mg daily	25 mg qd

MEMORIAL SLOAN-KETTERING CANCER CENTER
IRB PROTOCOL

[figure not shown]
IRB#: 14-140 A (7)

-1	400 mg daily	50 mg qd
1	400 mg daily	75 mg qd
2	400 mg daily	100 mg qd
3	400 mg daily	125 mg qd

Any adverse event that meets criteria in section 9.1 that occurs prior to the second cycle (i.e. before C2D1) will be considered a Dose Limiting Toxicity (DLT) for the purposes of dose escalation to the next dose level. Any adverse event that occurs after the first cycle may require a dose reduction for the patient but will not impact the assessment of dose level safety.

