14.0 BIOSTATISTICS

This is a multi institution single arm phase Ib/II trial to evaluate the clinical safety and efficacy of imatinib and BGJ398 in patients with advanced Gastrointestinal Stromal Tumors. Patients in the Phase Ib portion of the trial are required to have metastatic and or locally advanced GIST that has been treated with imatinib. Patients on the Phase II portion of the study are required to have advanced GIST and not have received any prior systemic therapy (untreated/treatment naïve).

Phase 1b Portion Study Design and Endpoint Assessment

The primary endpoint of the phase 1b portion of this study is to determine the maximum tolerated dose (MTD) and treatment schedule of BGJ398 administered in combination with imatinib in patients with GIST. The phase 1b will be pursued in standard 3+3 format, based on toxicities encountered during the first cycle of therapy.

The dose escalation schema is listed in Table 1. Dose escalation will proceed within each cohort according to Table 2. The first three patients will be enrolled at Dose Level 1. If dose level 1 is not found to be tolerable, then the next cohort will be enrolled at dose level -1. If dose level -1 is not found to be tolerable, then the next cohort will be enrolled at dose level -2. If dose level -2 is not found to be tolerable, then the study may be terminated based on discussions with the MSKCC Principal Investigator. If 0 or 1 of 6 patients experience a DLT on dose level 3, this will be the RP2D unless a lower dose is selected based on chronic tolerance of the combination and pharmacokinetic data. Lower dose levels may be expanded and an RP2D lower than the MTD may be selected based on safety and chronic tolerance considerations by the MSKCC Principal Investigator. If dose level 1 to -2 is identified as the MTD and concern exists regarding therapeutic activity of BGJ398 at this dose level, expansions with higher dose levels (1 to 3) may be considered at the MSKCC PI's discretion, with modification of the treatment schedule. When the RP2D is found, any patients from the Phase Ib portion of the study who remain on therapy below the MTD may have their BGJ398 dose increased to the MTD at the treating physician's discretion.

MEMORIAL SLOAN-KETTERING CANCER CENTER IRB PROTOCOL

IRB#: 14-140 A (7)

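### Table 2 names the level that fails the DLT rule as the MTD, and section 14.0 then permits raising phase Ib patients to that level

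*Combined protocol and SAP*

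**What the plan says.** Table 2 in section 9.1 has two stopping rows. If a level has 1 DLT in the first 3 patients and at least 1 more in the next 3, "then dose escalation is stopped, and this dose is declared the MTD". For 2 or more DLTs, the row reads "Dose escalation will be stopped. This dose level will be declared the MTD". The last row puts the RP2D at the level with at most 1 DLT in 6 "at highest dose level below the MTD".

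Elsewhere the protocol speaks of a tolerated dose. The phase Ib endpoint in section 9.1 is "to determine the maximum tolerated dose (MTD) and the Recommended Phase 2 Dose (RP2D"). Section 1.0 opens phase II "Once the highest tolerable dose is identified" or the clinical doses are reached. Section 9.1 describes a failed level as one that is not tolerable: "If dose level 1 is not found to be tolerable, then the next cohort will be enrolled at dose level -1".

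Section 14.0 adopts Table 2 for escalation. It adds that, once the RP2D is found, phase Ib patients "who remain on therapy below the MTD may have their BGJ398 dose increased to the MTD", at the treating physician's discretion.

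**The concern.** Under Table 2 the MTD is the level that failed. Under the endpoint wording it is the highest level that was tolerated. The two readings give different doses, and two things depend on which is used.

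The first is patient dosing. Section 14.0 sets the ceiling for dose increases at the MTD, not the RP2D. On the Table 2 meaning, that ceiling is a level the trial's own rule found not tolerable. DLTs are counted only in cycle 1, and section 1.0 says later events do not alter the assessment of a dose level, so toxicity after such an increase would not feed back into that assessment.

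The second is the reported result. The MTD is part of the phase Ib primary endpoint. Read literally, it would be reported one level above the highest level that passed.

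**Working it through.** The plan gives no figure to reproduce here. The check enumerates the outcomes of Table 2 and then applies section 14.0.

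**Inputs.** BGJ398 doses from Table 1: 25, 50, 75, 100 and 125 mg for levels -2, -1, 1, 2 and 3. Decision rules from Table 2. Dose-increase sentence and phase Ib maximum of 30 patients from section 14.0. Bar on re-increasing a reduced BGJ398 dose from the closing note of Table 7.

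**Step 1: label given to each outcome at one level.**

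| DLTs | Decision | Observed rate | Called the MTD? |
|---|---|---|---|
| 0/3 | escalate | 0% | no |
| 1/6 | escalate | 17% | no |
| 2/6, 3/6, 4/6 | stop | 33%, 50%, 67% | yes |
| 2/3, 3/3 | stop | 67%, 100% | yes |

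Every level that Table 2 calls the MTD has an observed rate of at least 2/6 = 33%. The highest passing level has at most 1/6 = 17%. If levels 1 and -1 both fail, Table 2 declares two MTDs.

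**Step 2: which meaning governs section 14.0.** The text before Table 2 refers forward to the MTD as defined there, section 14.0 says escalation follows Table 2, and no section redefines the term. The Table 2 meaning is therefore the operative one.

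**Step 3: apply the dose-increase sentence.** Suppose level 1 (75 mg) has 1/6 and level 2 (100 mg) has 2/6. Table 2 makes 100 mg the MTD and 75 mg the RP2D. A patient at 75 mg is below the MTD, so section 14.0 permits 100 mg.

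**Step 4: size of the increase.** From the level just below: (50−25)/25 = +100%; (75−50)/50 = +50%; (100−75)/75 = +33%; (125−100)/100 = +25%. Larger steps are possible, because the sentence covers any phase Ib patient below the MTD and the RP2D may itself be set lower: (125−75)/75 = +67%; (75−25)/25 = +200%. The ceiling is 125 mg in all cases.

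**Step 5: what the rates can bear.** Exact 95% intervals are 0.4% to 64.1% for 1/6, 4.3% to 77.7% for 2/6 and 9.4% to 99.2% for 2/3. They overlap heavily.

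**Step 6: how often one level would stop (assumption).** The documents give no DLT rate for the combination. For an assumed true rate p, P(stop) = P(X≥2 of 3) + P(X=1 of 3)·[1−(1−p)³]. At p = 0.30 this is 0.216 + 0.441 × 0.657 = 0.51. Over a range: 9% at p = 0.10, 29% at 0.20, 51% at 0.30, 69% at 0.40 and 83% at 0.50. This is per level and only shows that the condition is not remote.

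**The case against.** The strongest reply is that this is a terminology slip with one permissive sentence attached. Table 2 is consistent within itself, and its RP2D rule lands on a level with at most 1 of 6 DLTs. The increase is optional, reaches only those of at most 30 phase Ib patients who are still on therapy and not dose-reduced, and leaves the hold, reduce and stop rules of Table 7 in force. The 33% is also a cycle 1 rate in newly started patients, not the risk for someone already tolerating a lower dose.

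All of that stands, and it limits the weight of the point. It does not remove it. Discretion is not a cap when the protocol tells the physician that the ceiling is the MTD. Table 7 acts after toxicity has occurred, and its closing note protects only patients already reduced.

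A reader might infer that the statements allowing an RP2D below the MTD, and the Schedule B trigger, also contradict Table 2. They do not clearly do so. An RP2D below the MTD is what Table 2 produces, and concern about activity at a stopping level applies at least as much to the levels beneath it. The conflict rests on the three tolerated-dose statements quoted above.

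**Conclusion.** The concern holds, conditionally. If a level meets the stopping rule (at least 2 of 6, or at least 2 of the first 3), Table 2 calls that level the MTD, and section 14.0 permits unreduced phase Ib patients below it, including those at the RP2D, to be raised to it. The step is at least 25 mg (+25% to +100% from the level just below, more from lower levels) and never exceeds 125 mg. The observed rates at the boundary are at least 33% against at most 17%, and should not be read as estimates of risk.

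This rests on reading Table 2 as the operative definition, which sections 9.1 and 14.0 both support. The problem does not arise if no level on either schedule meets the rule. The sentence "If 0-1 of 6 patients experience a DLT on dose level 3, this will be the RP2D" covers the case where level 3 clears, but level 3 clearing on Schedule B would not cancel an MTD already declared on Schedule A.

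A reader might go further and infer that phase II patients would be treated at the failed level, or that the protocol requires the increase. The documents support neither: phase II uses the RP2D, and section 14.0 only permits the increase. It should be fixed because it concerns a primary-endpoint definition and a dosing ceiling.

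**What to change.** - In both stopping rows of Table 2, state that the level exceeds the MTD.
- Define the MTD, separately for each schedule, as the highest level with at most 1 of 6 DLTs (level 3 if it passes). Change the last row so that this level is itself called the MTD.
- In section 14.0, state that an increase may not exceed the MTD so defined for the patient's own schedule, or the RP2D if that was set lower for chronic tolerance on that schedule. Imply no switch of schedule.
- Check that the Schedule B trigger in sections 4.2, 9.1 and 14.0 still reads as intended. Under the new definition, level 1 as the MTD means that level 1 passed and level 2 failed. If level -2 fails, no level qualifies as the MTD, so the text should say whether Schedule B may then open.

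The cost is wording edits only, with no new patients, visits or procedures. When escalation stops for DLTs, the reported MTD will be one level lower than under the literal text.
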